5.3 Exclusion criteria

Patients eligible for this study must not meet **any** of the following criteria:

1. Radiotherapy of the pituitary <4 weeks before screening or patient who has not recovered from side effects
2. Patients with compression of the optic chiasm causing acute clinically significant visual field defect
3. Patients with Cushing's syndrome due to ectopic ACTH secretion
4. Patients with hypercortisolism secondary to adrenal tumors or nodular (primary) bilateral adrenal hyperplasia
5. Patients who have a known inherited syndrome as the cause for hormone over secretion (i.e. Carney Complex, McCune-Albright syndrome, MEN-1)
6. Patients with a diagnosis of glucocorticoid-remedial aldosteronism (GRA)
7. Patients who have undergone major surgery within 1 month prior to screening
8. Patients with known gallbladder or bile duct disease, acute or chronic pancreatitis (patients with asymptomatic cholelithiasis and asymptomatic bile duct dilation can be included)
9. Diabetic patients whose blood glucose is poorly controlled as evidenced by $\text{HbA}_{1\text{C}} > 8\%$
10. Patients who have clinically significant impairment in cardiovascular function or are at risk thereof, as evidenced by
 - congestive heart failure (NYHA Class III or IV), unstable angina, sustained ventricular tachycardia, clinically significant bradycardia, high grade AV block, history of acute MI less than one year prior to study entry
 - QTcF >450 msec at screening
 - History of syncope or family history of idiopathic sudden death
 - Risk factors for Torsades de Pointes such as uncorrected hypokalemia, uncorrected hypomagnesemia, cardiac failure
 - Concomitant disease(s) that could prolong the QT interval such as autonomic neuropathy (caused by diabetes or Parkinson's disease), HIV, cirrhosis, uncontrolled hypothyroidism, concomitant medication(s) with known risk for TdP
11. Patients with liver disease or history of liver disease such as cirrhosis, chronic active hepatitis B and C, or chronic persistent hepatitis, or patients with ALT or AST more than

2 x ULN, serum creatinine >2.0 x ULN, serum bilirubin >1.5 x ULN, serum albumin < 0.67 x LLN at screening

12. Patients who have any current or prior medical condition that can interfere with the conduct of the study or the evaluation of its results, such as

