Hepatic safety management:

If any of the criteria below are observed at any scheduled or unscheduled visit the sponsor should be notified immediately upon awareness.

- ALT or AST $> 3 \times \text{ULN}$ and Total Bilirubin $\geq 2 \times \text{ULN}$
- ALT or AST $> 5 \times \text{ULN}$ and $\leq 8 \times \text{ULN}$
- ALT or AST $> 8 \times \text{ULN}$

The following should be performed immediately within **72 hours** of awareness of the abnormality:

- Perform liver-directed medical history and physical examination (i.e. assess occupational hazards, concomitant medications including OTC meds, inter-current illness, etc)
- Liver chemistry tests: ALT, AST, total bilirubin, (fractionate to direct/indirect bilirubin if total bilirubin is $> 2.0 \times \text{ULN}$), Albumin, PT (INR), ALP, and GGT
- Perform hepatitis screen: anti-HAV, IgM (to confirm acute Hepatitis A), HbsAg, Anti-HBc, anti-HCV (if positive, PCR viral load should be assessed), Anti-HEV, ANA antibodies, anti-smooth muscle anti-bodies, CMV and EBV
- Perform abdominal ultrasound (liver and biliary tree)

Liver chemistry tests (LFTs) should be monitored every **3-4 days** until resolution or return to baseline status.

Patients or subjects may need to be discontinued if the abnormal liver function criteria are met upon LFT retesting (See discontinuation criteria [Section 7.1.3.1](#)). Progress reports of the event should be maintained until resolution or stabilization (i.e. no further elevation after 2 consecutive assessments).

[figure not shown]
For ALT or AST $> 5 \times \text{ULN}$ and $\leq 8 \times \text{ULN}$, the following must occur (in addition to the safety follow up procedures noted above)

- Study medication should be temporarily interrupted and liver chemistry tests monitored every **3-4 days** until resolution or return to baseline.
- If resolution or return to baseline does not occur after 2 weeks, the patient should be discontinued.
- If ALT or AST return to less than $5 \times \text{ULN}$ study drug can be resumed and patient can continue study per protocol.
- If ALT or AST rises above $5 \times \text{ULN}$ anytime after study drug is resumed, then study drug should be discontinued immediately.

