7.1.3.1 Criteria for premature patient withdrawal

Patients **may** voluntarily withdraw from the study or be dropped from it at the discretion of the investigator at any time.

Patients **must** be withdrawn from the study if any of the following occurs:

- Patients experiencing unacceptable drug-related toxicity (as described in [Table 6-1](#))
- Uncontrolled diabetes mellitus (DM), consistently high capillary glucose values in excess of 275 mg/dL (15.5 mmol/L), FPG \geq 240 mg/dL (13.3 mmol/L) or HbA_{1c} value \geq 10 % despite prior appropriate management and prior dose adjustment of the study drug,
- Patients experiencing adverse events in QTc:
 - a confirmed QTcF $>$ 480 msec and discontinuation recommended by a cardiologist, or
 - Mean QTcF $>$ 500 msec measured by triplicate ECGs and confirmed by a cardiologist
 - Significant arrhythmia findings from Holter monitoring such as:
 1. Any ventricular or supra-ventricular tachyarrhythmia associated with symptoms of hemodynamic compromise
 2. Sustained ventricular tachycardia ($>$ 30 sec) irrespective of symptoms
 3. Recurrent non-sustained VT (\geq 3 beats) during any 24-hour monitoring period
 4. Torsades de Pointes (TdP)
 5. Cardiac arrest
 6. Pause $>$ 5 seconds
 7. Second or third degree AV block
 - New occurrence of clinically significant/symptomatic bradycardia, or
 - Increased risk of QT prolongation by use of medications with known risk of TdP, or
 - Hypokalemia ($<$ 3.5 mmol/L) or hypomagnesaemia ($<$ 0.5 mmol/L) confirmed by repeat testing that is either a new finding or accompanied by vomiting or diarrhea and not corrected by treatment.
- Evidence of hypoadrenalinism: defined as an early morning (between 8 and 10 am) serum cortisol $<$ 3 μ g/dL and a mean 24h-UFC measurement $<$ LLN or symptoms suggestive of

hypoadrenalinism (e.g. postural hypotension, nausea, and abdominal pain) in association with a mean 24h-UFC measurement < LLN, which persist after drug dose adjustment

- Lack of efficacy: consistently elevated mean 24h-UFC level and lack of clinical benefit after ≥ 3 months treatment
- Pregnancy
- Patient experiencing
 - ALT or AST $> 3 \times$ ULN and Total Bilirubin $\geq 2 \times$ ULN and ALP $< 2 \times$ ULN
 - ALT or AST $> 5 \times$ ULN and $\leq 8 \times$ ULN persistent for more than 2 weeks
 - ALT or AST $> 8 \times$ ULN

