If any of those 3 discontinuation criteria are met, study medication should be discontinued immediately. In addition, proper safety follow-up management should be performed as outlined in [Section 6.2.1.1](#). Re-challenge of study medication is prohibited once discontinuation criteria are met.

If such withdrawal occurs, or if the patient fails to return for visits, the investigator must determine the primary reason for a patient's premature withdrawal from the study and record this information on the Study Completion CRF page. Patients may be withdrawn from the study prematurely for one of the following reasons:

[figure not shown]
- Adverse event(s)
- Abnormal laboratory value(s)
- Abnormal test procedure result(s)
- Protocol violation
- Subject withdrew consent
- Lost to follow-up
- Administrative problems
- Death

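### Protocol 6.2.1.1 says both that drug should be stopped and that it can be resumed when ALT/AST after 2 weeks is below 5 × ULN but neither resolved nor back to baseline, and Section 7.1.3.1 does not settle which applies

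*Protocol*

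**What the plan says.** Protocol 6.2.1.1 (Hepatic safety management) gives four bullets for ALT or AST above 5 and up to 8 × ULN.

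- **Bullet 1:** "Study medication should be temporarily interrupted and liver chemistry tests monitored every" 3–4 days, until values resolve or return to baseline.
- **Bullet 2:** "If resolution or return to baseline does not occur after 2 weeks, the patient should be discontinued".
- **Bullet 3:** if ALT or AST falls below 5 × ULN, "study drug can be resumed and patient can continue study per protocol".
- **Bullet 4:** if values rise above 5 × ULN again after drug is resumed, drug is stopped at once.

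For discontinuation, 6.2.1.1 also points to Section 7.1.3.1. The matching criterion there is ALT or AST in the same 5 to 8 × ULN band, "persistent for more than 2 weeks". The paragraph after the three liver criteria in 7.1.3.1 adds: "Re-challenge of study medication is prohibited once discontinuation criteria are met".

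The protocol does not define *resolution*. The nearest explanatory text is in the sentence on progress reports, which run "until resolution or stabilization (i.e. no further elevation after 2 consecutive assessments"). That explanation covers stabilization only.

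A note to Table 6-1 sends hepatic cases to 6.2.1.1, so the general adverse-event table is not a fallback.

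**The concern.** Bullets 2 and 3 use different yardsticks. Bullet 2 asks whether values have resolved or returned to baseline by 2 weeks. Bullet 3 asks only whether they are below 5 × ULN. A patient can fail the first test and pass the second. Section 7.1.3.1 uses a third yardstick, staying inside the band, and a patient who has dropped below 5 × ULN does not meet it.

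Two sites reading the same pages could therefore handle the same patient differently, one stopping for good and the other restarting. This is first a patient-safety matter. It also affects the data of a study whose primary objective is safety:

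- Under 6.2.2, permanent discontinuation makes the patient prematurely discontinued from the study.
- Under 10.5.2.1, the on-treatment period ends 28 days after the last dose, so stopping closes it and resuming extends it.
- Under SAP 4.8, exposure includes temporary interruptions, so for a patient who resumes the interruption itself counts as exposure.

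**Working it through.** The plan gives no figure to reproduce and no power calculation is involved. The check applies each rule to the ALT/AST value *x* (in × ULN) after 2 weeks.

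**Inputs**
- Baseline *b*: Section 5.3 excludes "patients with ALT or AST more than" 2 × ULN at screening. I take *b* ≤ 2. This is an assumption, because SAP 4.3 defines baseline as the last value before first dose.
- Bilirubin below 2 × ULN, so that the combined ALT/AST and bilirubin criterion in 7.1.3.1 is not met.

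**Rules**
- Bullet 2 stops the patient if *x* is not resolved and *x* > *b*.
- Bullet 3 allows resumption if *x* < 5.
- The 7.1.3.1 band criterion is met if 5 < *x* ≤ 8, persisting for more than 2 weeks.

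**Reading A: resolution means normal (*x* ≤ 1)**

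| *b* | *x* | Bullet 2 | Bullet 3 | 7.1.3.1 band | Result |
|---|---|---|---|---|---|
| 0.5 | 1 | no stop | may resume | not met | consistent |
| 0.5 | 1.5 | stop | may resume | not met | conflict |
| 1 | 4 | stop | may resume | not met | conflict |
| 2 | 2 | no stop | may resume | not met | consistent |
| 2 | 2.5 | stop | may resume | not met | conflict |
| 2 | 4.9 | stop | may resume | not met | conflict |
| 0.5, 1 or 2 | 5 | stop | no | not met | only bullet 2 acts |
| 0.5, 1 or 2 | 5.1 | stop | no | met | consistent |

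The conflict region is max(1, *b*) < *x* < 5. For *b* = 0.5 or 1 this is 1 < *x* < 5. For *b* = 2 it is 2 < *x* < 5. With *b* ≤ 2, the interval 2 < *x* < 5 lies in the conflict region for every eligible patient.

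**Reading B: resolution means *x* < 5**

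Bullet 2 then stops only *x* ≥ 5 and bullet 3 allows only *x* < 5, so no value falls under both and the conflict disappears. Two features of the text count against this reading:
- With *b* ≤ 2 < 5, any patient back at baseline is already below 5, so the alternative of returning to baseline in bullet 2 would add nothing.
- Bullet 1 runs the 3–4 day monitoring to the same endpoint, so monitoring could end at 4.9 × ULN.

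**Timing**

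Limiting bullet 3 to the first 2 weeks would not remove the problem. A patient at 4 × ULN on day 8 could be resumed under bullet 3. If still at 4 × ULN at 2 weeks, that patient then falls under bullet 2.

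**Boundary**

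Exactly 5 × ULN meets neither bullet 3 (below 5) nor the 7.1.3.1 band (above 5), whichever reading is taken.

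**The case against.** The best defence is that a consistent reading exists. Section 6.2.1.1 refers to 7.1.3.1 for discontinuation. Read through that criterion, bullet 2 covers the patient still in the band after 2 weeks, bullet 3 the patient who has left it, and bullet 4 the patient who re-enters it. This is a plausible account of the intent. It requires *resolution* to mean below 5 × ULN, which the protocol does not say, and it leaves the baseline wording in bullet 2 without effect. It does not cure the text.

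Four further points limit the finding, and all of them stand.

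- **Strength of wording.** A reader might infer two contrary orders. Bullet 3 is permissive, whereas bullet 2 says what should happen. An investigator who stops the patient breaches neither. The accurate statement is that one bullet permits what its neighbour advises against.
- **Re-challenge.** A reader might infer that resuming under bullet 3 is prohibited re-challenge. The prohibition follows a sentence about the three liver criteria of 7.1.3.1, and the patient described here meets none of them. Whether a stop under bullet 2 also carries the prohibition is unstated.
- **Who is affected.** A reader might infer that everyone above baseline at 2 weeks is caught. Bullet 2 is satisfied by resolution *or* return to baseline. A patient with baseline 0.5 and 0.9 × ULN at 2 weeks is above baseline but within normal limits, and is not stopped on either reading above.
- **Figure 6-3.** The liver algorithm could not be seen for this review and may show the deciding condition. The written bullets would still need to agree with it.

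**Conclusion.** The point holds in a limited form. For a patient from the 5 to 8 × ULN band who is below 5 × ULN after 2 weeks but neither resolved nor at baseline, bullet 2 calls for discontinuation, bullet 3 allows resumption, and the 7.1.3.1 band criterion does not require withdrawal. This rests on two assumptions: that *resolution* does not mean below 5 × ULN, and that no other 7.1.3.1 criterion applies.

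The conflict can arise for any eligible patient who enters the band, since 2 to 5 × ULN lies above any baseline within the screening limit. The documents give no basis for estimating how many patients that is.

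What can differ between sites is re-exposure after a liver signal, the count of hepatic discontinuations, and later time at risk. A reader might infer that the primary proportion is distorted by the index liver event. The documents do not support that. The event precedes the choice between stopping and resuming, so if it is recorded as a qualifying adverse event the patient is counted either way. Only later events could differ, through the longer or shorter on-treatment period. No sample size, power or error rate is involved. The protocol should be corrected because sites need one rule.

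**What to change.** - Define *resolution* in Protocol 6.2.1.1.
- Reconcile bullets 2 and 3 of 6.2.1.1 with the 5 to 8 × ULN criterion in 7.1.3.1, so that one stated condition decides between resuming and permanent discontinuation. Cover a value of exactly 5 × ULN.
- Check Figure 6-3 against the reconciled text and align it if it differs.
- State whether a discontinuation under bullet 2 falls under the re-challenge prohibition, which as written follows the three liver criteria of 7.1.3.1.

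Which condition to adopt is for the sponsor's clinical team. The cost is wording in one amendment or clarification letter, with no added assessments.

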6.2.2 Treatment interruption and treatment discontinuation

Patients experiencing unacceptable toxicity (AE grade 3 or higher) that the investigator considers directly attributable to pasireotide should have their dose reduced or should be withdrawn from the study. [Table 6-1](#) should be regarded as a guideline for the treatment of patients experiencing Adverse Events which are judged to be drug related. Any deviation from these guidelines should be discussed and approved by the sponsor.

Adverse events are described as mild (Grade 1), moderate (Grade 2), severe (Grade 3) or life-threatening (Grade 4). Guidelines for treatment of patients experiencing adverse events are indicated below ([Table 6-1](#)).

Table 6-1 Guideline for treatment of patients experiencing adverse events

Patients	Adverse event	Action
All	AE grade \leq 2 (mild to moderate)	No drug adjustments
	AE grade \geq 3 (severe to life-threatening) and judged as drug related* [#]	Reduce dose by 300 μ g b.i.d. If AE improves to grade \leq 2 within 1 week, increase dose by 300 μ g b.i.d. If AE recurs at grade \geq 3, reduce dose by 300 μ g b.i.d. again and remain at lower dose. If AE does not improve to grade \leq 2 within 1 week on lower dose, reduce dose by 300 μ g b.i.d. again if possible. If AE does not improve to grade \leq 2 within 1 week on 300 μ g b.i.d., patient is to discontinue treatment. For patients experiencing hyperglycemia, the dose should be reduced if the severity grade 3 or greater persists despite appropriate management.* If the hyperglycemia is considered to be life-threatening, the patient should be withdrawn regardless of anti-diabetes treatment.

* CTCAE v3.0 grades diabetes that is treated with insulin as a grade 3. However, diabetes grade 3 will require a study drug dose reduction only in cases of uncontrolled hyperglycemia despite of appropriate management.

[#] No dose reductions are required in case of a QT prolongation but guidelines for QT monitoring and discontinuation criteria must be observed.

Note: for hepatic safety management follow [Section 6.2.1.1](#).

If a patient permanently discontinues study treatment, the patients will be considered as prematurely discontinued from the study. Patients will have to perform a study phase completion evaluation on the day of the last study drug administration (refer to Study Phase Completion evaluation in [Table 7-1](#)).

Patients must be transitioned to commercial pasireotide within 6 weeks after approval and reimbursement in each respective country. Patients who complete the study because they are transitioned to commercial pasireotide are considered completed and will have to perform a study phase completion evaluation on the day of the last study drug administration (refer to Study Phase Completion evaluation in [Table 7-1](#)).

Patients who are treated until 31 December 2015 (until 31 December 2016 for sites in South Korea and Brazil) will be considered as completed patients. They will have to perform a study phase completion evaluation on the day of the last study drug administration (refer to Study Phase Completion evaluation in [Table 7-1](#)).

6.3 Concomitant medications

All medications, including over the counter medications (OTC), taken prior to the first study drug administration and which continue after visit 2 (beginning of the treatment) are to be recorded on the Concomitant Medication section of the CRF.

However, investigators should discourage patients from taking any medication during the study, with the exception of medications that are required to treat an adverse event.

6.3.1 Permitted concomitant therapy

The patient must be told to notify the investigational site about any new medications he/she takes after the start of the study drug. All medications (other than study drug) and significant non-drug therapies (including physical therapy and blood transfusions) administered during the study must be listed on the Concomitant Medications or the Procedures and Significant Non-Drug Therapies CRF, respectively.

Diabetic patients must continue their treatment for diabetes throughout the study as indicated by their physician/diabetes specialist.

6.3.2 Prohibited concomitant therapy

Rosiglitazone and pioglitazone treatment are not permitted during the study as they could affect the patient's ACTH levels.

Further, the use of concomitant medications with known risk of TdP is prohibited and requires the discontinuation of the patient prior to starting the respective medication with known risk of TdP. The list of updated medications with known risk of TdP can be found at the following link: <http://crediblemeds.org/>

6.4 Patient numbering, treatment assignment and randomization

6.4.1 Patient numbering

Each patient is identified in the study by a Subject Number (Subject No.), that is assigned when the patient is first enrolled for screening and is retained as the primary identifier for the patient throughout his/her entire participation in the trial. The Subject No. consists of the Center Number (Center No.) (as assigned by Novartis to the investigative site) with a sequential patient number suffixed to it, so that each subject is numbered uniquely across the entire database. Upon signing the informed consent form, the patient is assigned to the next sequential Subject No. available to the investigator. Once assigned, the Subject No. must not be reused for any other subject and the Subject No. for that individual must not be changed, even if the patient is re-screened.

If the patient fails to be assigned to treatment for any reason, the reason will be entered into the Screening Disposition page.

6.4.2 Treatment assignment and randomization

Randomization is not applicable in the study.

[figure not shown]
6.4.3 Treatment blinding

This is an open-label study and blinding is not applicable.

6.5 Study drug supply

6.5.1 Study drug preparation and dispensation

Novartis will supply the investigational drug in 1 ml ampoules containing 900 µg, 600 µg, or 300 µg pasireotide per 1 ml of solution.

Patients must be able to self-administer the study drug (subcutaneous injections) and are to receive instruction from the site staff or investigator on the correct procedures. They should be advised to avoid multiple injections at, or near the same site. Ampoules may not be re-used; a new ampoule should be used for each injection. Patients should be instructed to retain and return unused ampoules at their next scheduled visit.

All dosages prescribed to the patient and all dose changes during the study must be recorded on the Dosage Administration Record CRF.

6.5.2 Study drug packaging and labeling

Medication labels will be in the local language and comply with the legal requirements of each country. They will include storage conditions for the drug but no information about the patient.

6.5.3 Drug supply and storage

Study treatments must be received by a designated person at the study site, handled and stored safely and properly, and kept in a secured location to which only the investigator and designated assistants have access. Upon receipt, pasireotide should be stored according to the instructions specified on the drug labels.

6.5.4 Study drug compliance and accountability

6.5.4.1 Study drug compliance

The investigator should instruct the patient to take the study drug exactly as prescribed (promote compliance).

Compliance will be assessed by the investigator and/or study personnel at each patient visit and information provided by the patient and/or caregiver will be captured in the Drug Accountability Form. This information must be captured in the source document at each patient visit.

6.5.4.2 Study drug accountability

The investigator or designee must maintain an accurate record of the shipment and dispensing of study treatment in a drug accountability ledger. Drug accountability will be noted by the field monitor during site visits and at the completion of the study. Patients will be asked to return all unused study treatment and packaging on a regular basis.

At study close-out, and, as appropriate during the course of the study, the investigator will return all used and unused study treatment, packaging, drug labels, and a copy of the completed drug accountability ledger to the Novartis monitor or to the Novartis address provided in the investigator folder at each site.

